13.4. Immunoglobulin

Blood samples for assessment of immunoglobulins (IgM, IgG and IgA) will be collected at the time points specified in the [APPENDIX 1](#). Descriptive statistics for actual values and changes

from baseline to each scheduled post-baseline visit will be presented by immunoglobulin tests and treatment group for the Safety population. Any values BLQ will be set to this limit for analysis. All data of immunoglobulin will be listed by treatment group, visit and test. In the case when duplicated measurements of immunoglobulins are recorded within the same visit, the highest value will be used for analysis in a conservative approach.

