Route of Administration: CT-P10 or Rituxan 375 mg/m ² diluted in normal saline will be administered as an IV infusion weekly for 4 weeks during the Induction Study Period. CT-P10 or Rituxan (375 mg/m ² IV) will be administered as maintenance in patients who have a disease control (complete response [CR], unconfirmed complete response [CRu], partial response [PR] or stable disease [SD]) after the completion of the Induction Study Period. The Maintenance Study Period will be continued up to maximum 12 cycles for 2 years, with study drug (either CT-P10 or Rituxan) administered every 8 weeks for a maximum of 6 cycles for 1 year. After the 1 st year of Maintenance Period (MP1), once the similarity between study drugs is confirmed, additional CT-P10 administration will be offered to all patients who have completed MP1 at discretion of participating investigator. The total infusion of the maintenance treatment will not exceed 12 cycles over 2 years.
Objectives: Primary Objective: To demonstrate that CT-P10 is similar to Rituxan in terms of efficacy as determined by overall response rate (CR + CRu + PR) at 7 months (Prior to Cycle 3 of the Maintenance Study Period) according to the Modified Response Criteria for Malignant Lymphoma.

Secondary Objectives:

- To evaluate overall response rate (CR + CRu + PR) according to the Modified Response Criteria for Malignant Lymphoma during the study period.
- To evaluate additional efficacy parameters (progression-free survival, time to progression and overall survival according to the Modified Response Criteria for Malignant Lymphoma).
- To evaluate pharmacokinetics, pharmacodynamics (B-lymphocyte [B-cell] kinetics), overall safety including immunogenicity, and biomarkers of CT-P10 in comparison with Rituxan.

Patient Population: Male or female patients 18 years or older, with a histologically confirmed FL of grade 1 to 3a (according to the World Health Organization 2008 classification); Ann Arbor stage II, III or IV disease; low tumour burden; at least 1 measurable tumour mass; confirmed CD20+ lymphoma; Eastern Cooperative Oncology Group performance status of 0 to 1; and adequate bone marrow, hepatic, and renal function reserve.

[figure not shown]

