4. OVERALL STUDY DESIGN AND PLAN

This is a Phase 3, prospective, randomized, parallel-group, active-controlled, double-blind, multicenter, international study to evaluate the similarity of efficacy and safety of CT-P10 to Rituxan in patients with Grade 1 to 3a (Ann Arbor stage II-IV) low tumour burden follicular lymphoma (LTBFL) based on Groupe d'Etudes des Lymphomes Folliculaires (GELF) criteria. The study will include study centers in Europe, Africa, the Middle East, Asia Pacific, and Latin and North America.

The study will consist of 4 periods: Screening Period, Induction Study Period, Maintenance Study Period, and Follow-up Period. The overview of study design is shown in [Figure 1](#).

Figure 1: Schematic of Study Design

- Screening Period (up to 6 weeks)
- Induction Study Period (up to 4 weeks):
 - Study drug will be administered weekly for 4 weeks (at a dose of 375 mg/m² by an intravenous [IV] infusion).
 - The End of Treatment (EOT) 1 visit will occur 1 week (±1 day) after the last dose of study drug administration in the Induction Study Period.
 - Patients will be assessed 8 weeks (±7 days) after the last dose of study drug administration in the Induction Study Period, and the investigator will determine whether patients qualify to continue in the Maintenance Study Period.
 - Patients who experienced CR, CRu, PR, or stable disease (SD) in this assessment will qualify for the Maintenance Study Period and the assessment visit will be called the Maintenance 1 visit.
 - Patients who experienced progressive disease (PD) or unknown status of disease will not enter into the Maintenance Study Period. These patients will be withdrawn from the study treatment and will enter the Follow-up Period, provided patient consent has not been withdrawn. For these patients, the assessment visit will be called the EOT2 visit.

- If a patient withdraws before the completion of the Induction Study Period, this patient will not enter the Maintenance Study Period. However, the patient will enter the Follow-up Period, provided patient consent has not been withdrawn.
- Maintenance Study Period (up to maximum 12 cycles for 2 years):
 - The first dose in the Maintenance Study Period will be administered 8 weeks (± 7 days) after the last dose of study drug administration in the Induction Study Period.
 - Study drug will be administered every 8 weeks up to maximum 12 cycles for 2 years (at a dose of 375 mg/m^2 by an IV infusion).

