 - The first year of Maintenance Period (MP1) consists of 6 cycles of maintenance therapy (Maintenance Cycles 1 to 6) and the second year of Maintenance Period (MP2) consists of 6 cycles of maintenance therapy (Maintenance Cycles 7 to 12). After MP1, once the similarity between study drugs is confirmed, additional treatment with CT-P10 will be offered to all patients who have completed MP1 at discretion of the investigator.
 - The EOT3 visit will occur 8 weeks (± 7 days) after the last dose of study drug administration in the Maintenance Study Period.
 - Patients who complete the Maintenance Study Period will enter the Follow-up Period. A patient will be considered as having completed the study treatment if:
 - The patient could have entered but did not continue on the MP2 and completed all visits of the MP1 (total 6 cycles).
 - The patient continued on the MP2 and completed all visits of the MP1 and MP2 (total 12 cycles).
 - If a patient withdraws before the completion of the Maintenance Study Period, the patient will enter the Follow-up Period, provided patient consent has not been withdrawn.
 - If a patient is terminated within 6 months from Day 1 of Cycle 1 of the Induction Study Period, the EOT3 visit will occur within 4 to 8 weeks (± 7 days) after the last dose of study drug administration in the Maintenance Study Period.
- Follow-up Period (up to 27 months from Day 1 of Cycle 1 of the Induction Study Period for the last enrolled patient):
 - During the Follow-up Period, patients will be monitored every 6 months (± 2 weeks) for disease status until treatment with new anticancer therapy or disease progression, and

every 3 months (± 2 weeks) for survival and salvage treatment until death or study termination.

The end of study is defined as the date of the database is locked. The schedule of events is presented in [APPENDIX 1](#).

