5. GENERAL STATISTICAL CONSIDERATIONS

Continuous data will be summarized using descriptive statistics: n, mean, standard deviation, minimum, median, and maximum, unless otherwise specified. Minimum and maximum will be presented to the same number of decimal places as reported, mean and median will be presented to one more decimal place than the reported. Standard deviation will be presented to two more decimal places than the raw data. If the geometric mean and percent coefficient of variation (CV%) are to be presented, geometric mean will be set to the same decimal places as the mean and CV% will be set to the one less decimal places than the standard deviation. If interquartile range (IQR) is to be presented, it will be displayed along with 25th and 75th quartile in same decimal place with median. Confidence interval (CI) obtained from statistical procedures will be displayed to two decimal places. P-values will be presented to three decimal places. If a p-value is less than 0.001, it will be reported as “< 0.001”. If a p-value is greater than 0.999 it will be reported as “> 0.999”.

Categorical data will be summarized using numbers and percentages of patients. Percentages will be presented to one decimal place and will be suppressed when the count is zero. The denominator for all percentages will be the number of patients within each treatment group for the population of interest, unless otherwise specified.

Tables summarized by visit will be conducted for all scheduled visits including EOT1, EOT2, EOT3 and excluding Follow-up visits. EOT2 and Maintenance Cycle 1 will be combined.

All data will be displayed in listings. Unless otherwise specified, listings will be sorted by the treatment group, patient number, and assessment date or visit date, if applicable. In cases where more ordering is required, other variables will be included in the sort order as applicable.

When combining data from electronic Case Report Form (eCRF) and analytical facilities such as [REDACTED], discrepancy will be handled as following:

- 1) Recorded as sample collected in eCRF but no corresponding results from analytical facility – listing will display only the sample collection date/time from eCRF and the data will be summarized in ‘Missing’ category, if applicable.

- 2) No records in eCRF which corresponds to the results from analytical facility – listing will display sample collection date/time and results from analytical facility.

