13.2.2. Clinical Chemistry

The following chemistry laboratory tests will be included: Alanine aminotransferase (ALT) (U/L), Albumin (g/L), Alkaline phosphatase (U/L), Aspartate aminotransferase (AST) (U/L), Blood urea nitrogen (mmol/L), Calcium (mmol/L), Creatinine (μ mol/L), Glucose (mmol/L), Lactate dehydrogenase (IU/L), Potassium (mmol/L), Sodium (mmol/L), Total bilirubin (μ mol/L), Total protein (g/L) and Uric acid (mmol/L).

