17. HBsAg, HBsAb, and HBcIg should be assessed within 42 days before the first drug administration in all patients (mandatory). If the result is HBsAg (positive), the patient should be excluded from the study. For patients whose HBsAg is negative, HBsAb is negative or positive, and HBcIg is positive, a DNA test should be performed within 42 days before the first drug administration. If the DNA test result is positive, the patient should be excluded from the study and if the DNA test result is negative, the patient can be included. For the patients enrolled based on the DNA test, the DNA test will be done every 24 weeks (± 8 weeks) for monitoring purposes until the patient receives new anticancer therapy. If hepatic symptoms are suspicious (ie, AST ≥ 3 times the ULN, ALT ≥ 3 times the ULN, or total bilirubin ≥ 2 times the ULN) during the Induction Study Period and Maintenance Study Period, then HBsAg, HBsAb, HBcIg, and DNA should be tested. Hepatitis C virus antibody and HIV antibody must be obtained within 42 days before the first study drug administration for all patients. Hepatitis and HIV testing will be performed at the local laboratory.
18. Immunoglobulin (IgG, IgM, IgA) testing and immunogenicity (antiriximab antibodies) testing will be obtained prior to the beginning of study drug of the Induction Study Period. Immunoglobulin testing will also be obtained at the EOT1 visit and before administration on Day 1 of Cycle 1 (Month 3; EOT2), Cycle 2 (Month 5), and Day 1 of Cycle 3 (Month 7) during the Maintenance Study Period. Immunogenicity testing will also be obtained prior to Day 1 of Cycle 1 (Month 3; EOT2), Cycle 3 (Month 7), and Cycle 6 (Month 13) and Cycle 9 (Month 19) during the Maintenance Study Period and at the EOT3 visit. Immunoglobulin and Immunogenicity testing must be completed before administration of the study drug at each planned visit and any time during the EOT visit. Immunoglobulin and Immunogenicity testing will be performed at the central laboratory. If a patient is terminated within 6 months from Day 1 of Cycle 1 of Induction Study Period, immunogenicity should be assessed at EOT2 (Month 3), EOT3 and the first follow-up visit.

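### SAP Section 13.4 summarises IgG, IgA and IgM without counting the patients in each arm who fall below normal, and no sample is scheduled after Month 7

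*SAP*

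**What the plan says.** **Summary.** SAP Section 13.4 provides descriptive statistics for observed IgM, IgG and IgA and for changes "from baseline to each scheduled post-baseline visit will be presented by immunoglobulin tests and treatment group for the Safety population". All values are also listed. Section 5 defines the default content: "Continuous data will be summarized using descriptive statistics: n, mean, standard deviation, minimum, median, and maximum, unless otherwise specified". Section 13.4 does not override it and gives no reference limit, threshold, category count or shift table.

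**Handling rules.** Section 13.4 sets values below quantification to the quantification limit. Where a visit has duplicates it takes the highest, and calls that choice conservative. Section 13 lists unscheduled results without summarising them; the only exception is the CTCAE analysis of laboratory data.

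**Sampling.** Appendix 1, footnote 18, schedules immunoglobulin samples before the first Induction dose, at EOT1, at Maintenance Cycle 1 (or EOT2), and then at "Cycle 2 (Month 5), and Day 1 of Cycle 3 (Month 7) during the Maintenance Study Period". It adds that "Immunoglobulin and Immunogenicity testing must be completed before administration of the study drug at each planned visit". Appendix 2 gives the same visits and shows none at Maintenance 6, Maintenance 9 or EOT3.

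**The concern.** Section 13 names immunoglobulin testing among the safety assessments. For a B-cell-depleting antibody, the result of interest is a patient whose level drops to an abnormally low value. That is a statement about individuals in the low tail, and group statistics by visit answer it only indirectly. Elsewhere the SAP does categorise patients:

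- worst CTCAE grade and shift tables for haematology and chemistry (Section 13.2)
- shift tables for urinalysis (13.2), ECG (13.6) and physical examination (13.9)
- counts of notable vital signs (13.7)

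Immunoglobulins have no equivalent, and Appendix 3, which drives the CTCAE grading, has no immunoglobulin row.

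What is at stake is one part of the safety comparison. The report could not say, from a table, whether the proportion of patients with low IgG, IgA or IgM is similar between arms. A reader could also take the table to describe the whole treatment course when it stops at Month 7.

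**Working it through.** **1. What each planned statistic can show**

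| Planned item | What it tells about low values |
|---|---|
| Mean, median | Centre of the group |
| SD | Spread, without direction or a count |
| Minimum | The single lowest patient at that visit |
| Listing | Every value, but the reader must do the counting |
| Number below normal | Not planned |
| Shift from baseline category | Not planned |

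All tabulated statistics are per visit. None combines a patient's visits into a lowest post-baseline value, so a patient who is low at only one visit is not identified as having ever been low.

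**2. Effect of the handling rules on a count of low patients**

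- Highest duplicate: if one of two values at a visit is below the limit and the other is not, the patient is classed as normal. The rule moves the result away from the harm of interest.
- Unscheduled results: a low value found between visits would be left out unless the new table says otherwise.
- Values set to the quantification limit: this raises the mean and minimum, but does not change a count below normal provided the quantification limit lies below the lower limit of normal (assumption; neither figure is in the documents).

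**3. Infusions after the last scheduled sample**

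Inputs:

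- Induction: "Study drug will be administered weekly for 4 weeks", so 4 infusions (SAP Section 4).
- Maintenance: "The total infusion of the maintenance treatment will not exceed 12 cycles over 2 years" (Protocol Synopsis), so at most 12.
- Split: the first maintenance year (MP1) has Cycles 1 to 6; the second (MP2) "consists of 6 cycles of maintenance therapy (Maintenance Cycles 7 to 12" (SAP Section 4).
- Last sample: predose at Maintenance Cycle 3, week 28.

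The documents do not state a total number of infusions, so it is derived here.

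- Before the last sample: 4 Induction + Maintenance 1 and 2 = 6.
- Up to the end of MP1: 4 + 6 = 10 in total; 10 − 6 = 4 afterwards (40%).
- With a full MP2: 4 + 12 = 16 in total; 16 − 6 = 10 afterwards (10/16 = 62.5%).

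In time, Maintenance Cycle k falls at week 12 + 8(k − 1). Cycle 3 is at week 28, Cycle 12 at week 100, and EOT3 at week 108. For a patient who completes MP2, 108 − 28 = 80 of 108 weeks (74%) follow the last scheduled sample.

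**4. Consequence for MP2**

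Section 13 says that in the final report all safety analyses will also be run on the Safety population – 2nd Maintenance Period subset. For immunoglobulins that subset has no scheduled result from MP2 itself. Any such table would describe samples taken before MP2 began, and so before Rituxan patients moved to CT-P10.

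**The case against.** **The planned statistics are not only means.** This stands. A reader might infer that the planned tables would hide a difference in the low tail between two arms with equal mean change. The documents do not support that. If a few patients in one arm had large falls while the other arm had a small uniform fall, the SD and minimum of the change would differ, and usually the median too. What is missing is narrower: the number of patients affected.

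**All values are listed.** True, so nothing is lost from the record. A listing is still not a comparison by arm.

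**The clinical consequence is covered elsewhere.** Infections are an adverse event of special interest and are summarised by study period, including MP2. A low level reported as an adverse event would also be tabulated. This reduces the importance of the gap. A reader might infer that the missing count leaves infection risk unassessed; it does not, and the documents state no link between immunoglobulin level and infection.

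**The Month 7 limit is a sampling decision.** Correct. Appendices 1 and 2 agree, so there is no contradiction, and SAP wording cannot create later samples. The point on timing is therefore one of disclosure.

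**Ten of 16 is the maximum case.** Also correct. MP2 is optional, and all its dosing is CT-P10. In the period when the two products are given side by side, the figure is 4 of 10.

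**No reference range is given.** Immunoglobulins are tested centrally, while the normal ranges noted under Appendix 3 come from local laboratories. A central range must be obtained before the count can be produced.

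**Conclusion.** The point holds as a gap in safety reporting. Section 13.4 yields no count, by arm, of patients whose IgG, IgA or IgM falls below normal, although the SAP gives categorical tables to comparable safety data. The SD and minimum point towards a low tail but cannot size it. The rule for duplicates works against detecting a fall and is not conservative for that purpose.

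On timing, up to 4 of 10 infusions up to the end of MP1, and up to 10 of 16 with a full MP2, follow the last scheduled sample. No immunoglobulin conclusion can be drawn for MP2. A reader might infer that the schedule is an error or that the biosimilarity conclusion is at risk; nothing in the documents supports either reading, and the primary endpoint is untouched.

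The verdict assumes that the central laboratory has a reference range, and that the table shells, a separate addendum not seen here, do not already include a low-value count.

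**What to change.** In SAP Section 13.4:

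1. Add, by arm and separately for IgG, IgA and IgM, the number (%) of patients with any post-baseline value below the central laboratory's lower limit of normal. State the denominator.
2. Add a shift table from baseline category (normal or low) to lowest post-baseline category.
3. For this table, take the lowest of any duplicates and include unscheduled results, as Section 13.2 already does for CTCAE grading. The descriptive table can keep its present rules, but the description of the highest duplicate as conservative should be removed or justified.
4. State in the report that no immunoglobulin sample is scheduled after Month 7 (predose at Maintenance Cycle 3), give the 4 of 10 and 10 of 16 figures as maxima, and say that no immunoglobulin conclusion is drawn for MP2.

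The cost is one extra table from samples already planned, a few sentences of text, and a request to the central laboratory for its reference range. Sampling, dosing and patient management do not change.

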5.5. Definition of Baseline

The baseline value will be considered to be the last non-missing value before the first administration of study drug. Post-baseline values will be considered to be all values collected after the first administration of study drug.

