13.1.5. Treatment-Emergent Adverse Events of Special Interest

The following will be considered as AEs of special interest: infusion-related reactions (IRR), infections and progressive multifocal leukoencephalopathy (PML).

TEAEs of IRR will be determined if the information is recorded as IRR in the ‘Adverse Events’ page of the eCRF. TEAEs of infections will be determined if a SOC is ‘Infections and infestations’. Although PML is an AE of special interest, it is captured only by a PT ‘Progressive multifocal leukoencephalopathy’. Therefore, TEAEs of PML will be included in the summary of TEAEs instead of generating an additional table.

All TEAEs of IRR and infections will be listed separately including variables detailed in [Section 13.1](#). With variables detailed in [Section 13.1](#), the listing will include information recorded on the ‘Adverse Events’ and ‘Infusion related/Anaphylactic Reaction’ page of eCRF will be included: start/stop time of IRR; signs and symptoms; whether symptoms are experienced (no, yes with

specified intensity NCI CTCAE); the lowest blood pressure (BP) level after study drug exposure [mmHg] and date/time of BP assessment (if BP is decreased after study drug exposure); comments on IRR.

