The number and percentage of patients with CTCAE grade greater than or equal to 3 will be summarized by laboratory category, CTCAE term, grade and treatment group for the Safety population and Safety population – 2nd Maintenance Period subset. The summary will be presented in Overall and by each study period (up to MP1, MP2). Only the most severe case of the post-baseline during unscheduled and scheduled visits will be included.

The number and percentage of patients with CTCAE grade will be provided, by laboratory category, CTCAE term, grade and treatment group for the Safety population and Safety population – 2nd Maintenance Period subset, in the form of a shift table to detect changes from baseline. The summary will be presented in Overall and by each study period (up to MP1, MP2). Only the most severe case during unscheduled and scheduled visits will be included for the post-baseline result.

All hematology and clinical chemistry data will be listed by treatment group. Results of CTCAE will be presented by separate listing.

Result interpretation for all urinalysis parameters will be collected as {'Normal', 'Abnormal, not clinically significant' and 'Abnormal, clinically significant'}. The number and percentage of patients with urinalysis results will be provided, by parameter, visit and treatment group for the Safety population, in the form of a shift table to detect changes from baseline.

All urinalysis data will be listed by treatment group, visit and parameter.

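### SAP 13.4 analyses the highest of duplicate immunoglobulin results and calls this conservative; for post-baseline values it works the other way (minor)

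*SAP*

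**What the plan says.** SAP 13.4 plans by-visit descriptive statistics for IgM, IgG and IgA, as actual values and as change from baseline, by treatment group in the Safety population. Two handling rules apply:

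- Duplicates: if a visit has more than one result for the same immunoglobulin, the SAP states that "the highest value will be used for analysis in a conservative approach". The section does not say in which direction this is meant to be conservative.
- Results below quantification: "Any values BLQ will be set to this limit for analysis".

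The section also provides that "All data of immunoglobulin will be listed by treatment group, visit and test".

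SAP 5.5 sets baseline for all variables: "The baseline value will be considered to be the last non-missing value before the first administration of study drug". Section 13.4 does not say which rule governs when there are two predose results.

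For CTCAE-graded laboratory data, SAP 13.2 takes the worst result. Of the shift tables it says: "Only the most severe case during unscheduled and scheduled visits will be included for the post-baseline result". Appendix 3, which lists the graded parameters, has no immunoglobulin term.

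**The concern.** In a safety analysis, conservative should mean not understating harm. The documents do not name the harmful direction for immunoglobulin, but they point one way:

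- B-cell kinetics is the pharmacodynamic endpoint.
- The protocol synopsis lists lymphopenia and infection among the common reactions to the reference product.
- SAP 13.1.5 makes infections and PML events of special interest.
- Immunoglobulin testing is itself a safety assessment.
- Nowhere is a rise in immunoglobulin treated as a concern.

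On that reading the higher of two post-baseline results is the less worrying one, and the rule selects it. The descriptive tables are the only planned summaries of immunoglobulin: no grade, shift table or count of low values would bring a low duplicate back into view. The below-quantification rule also acts upward, so a result below the limit that has a measurable duplicate drops out of the tables.

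At stake are the accuracy of the reported levels and changes, and the possibility that the study report claims a safeguard that the rule does not give. No efficacy endpoint is involved.

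**Working it through.** The plan gives no figure for this rule, so there is none to reproduce. The size follows from a standard result.

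**Inputs.** The highest-value rule and its restriction to same-visit duplicates come from SAP 13.4; the baseline rule comes from SAP 5.5. Three inputs are assumptions, because the documents do not give them: two readings with independent normal error; a within-visit CV of 5% to 20%; and duplicates at 2% to 25% of visits.

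**Bias in one duplicated result.** Let X and Y be two readings of a true level μ with SD s. The maximum is (X + Y)/2 + |X − Y|/2. The difference X − Y has SD s√2, so E|X − Y| = s√2 × √(2/π) = 2s/√π. Hence

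- E[max] = μ + s/√π = μ + 0.564s
- E[min] = μ − 0.564s
- E[mean] = μ

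| Assumed CV | Highest | Mean | Lowest |
|---|---|---|---|
| 5% | +2.8% | 0 | −2.8% |
| 10% | +5.6% | 0 | −5.6% |
| 15% | +8.5% | 0 | −8.5% |
| 20% | +11.3% | 0 | −11.3% |

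Simulation with 2,000,000 pairs per CV agrees with these values.

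**Change from baseline.** Take an illustrative true fall of 20% (baseline 1.0, follow-up 0.8) and a CV of 10%, so the maximum multiplies a level by 1.0564 on average.

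- Duplicates at follow-up only: 0.8 × 1.0564 − 1 = −0.155, a fall of 15.5%.
- Duplicates at baseline only: 0.8 − 1.0564 = −0.256, a fall of 25.6%.
- Duplicates at both: 0.8 × 1.0564 − 1.0564 = −0.211, a fall of 21.1%.

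The same rule understates the fall in the first case and overstates it in the other two.

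**Group mean.** The shift is the share of duplicated results times 5.64% (CV 10%):

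- 2% duplicated: 0.1%
- 5% duplicated: 0.3%
- 10% duplicated: 0.6%
- 25% duplicated: 1.4%

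**Comparison between arms.** With a common s, the difference in arm means shifts by 0.564s × (share duplicated with CT-P10 − share duplicated with Rituxan). This is zero when the shares are equal.

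**Baseline.** With two predose results, 5.5 selects the later and 13.4 the higher. They disagree whenever the earlier result is the higher.

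**The case against.** The strongest case against is that the rule does little. It applies only to duplicates, treats both arms alike and enters descriptive tables that drive no test or decision. Infections are analysed directly and are untouched. All of this stands, and it sets the severity. It does not make the label correct or settle the baseline.

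A reader might also infer more than the documents support:

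- **That low values are hidden.** They are not. Every immunoglobulin result is listed, so the lower duplicate remains visible there. Only the value entering the summary tables is affected.
- **That the arms are pulled toward similarity.** This would need unequal duplicate rates, or repeats triggered by low readings that are commoner in one arm. The documents show neither. Similarity is claimed on overall response rate, and immunoglobulin has no between-arm test.
- **That samples are repeated because the first reading was low.** The documents do not say why duplicates arise. Samples are taken at fixed visits and tested centrally, and SAP 13 keeps unscheduled results out of summaries apart from CTCAE grading. A redraw recorded as unscheduled would not enter these tables.
- **That 13.4 contradicts 13.2.** The worst-result rule in 13.2 covers CTCAE grades. The by-visit descriptive statistics in 13.2, which are the true counterpart of 13.4, carry no such rule. The contrast shows what the SAP regards as worst case elsewhere, and no more.
- **That the lowest value should simply replace the highest.** In a descriptive mean that swaps a bias of +0.564s for one of −0.564s.

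**Conclusion.** The rule is mislabelled and needs changing, as a minor point. For post-baseline values it is anti-conservative: about 0.56 measurement SD upward per duplicated result, or 2.8% to 11.3% for assumed CVs of 5% to 20%. For change from baseline the net direction depends on where the duplicates fall, so the rule is not conservative in any consistent sense. Group means move little if duplicates are rare. The unclear precedence between 13.4 and 5.5 is a separate gap in specification.

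This rests on two things: the inference that a fall is the direction of concern, and independent normal error between duplicates. Positively correlated errors of equal variance would make the bias smaller. Neither the CV nor the frequency of duplicates is known. The primary endpoint and the similarity conclusion are unaffected.

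**What to change.** In SAP 13.4:

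1. Replace the highest-value rule with the mean of same-visit duplicates, or with a pre-set first or last valid result, at every visit.
2. State that SAP 5.5 governs baseline, and say how duplicate predose results are resolved.
3. Delete the description of the rule as conservative.
4. If a worst-case view is wanted, add a supplementary summary using the lowest post-baseline value, labelled as such.

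The main change costs a short text edit and one programming line, with no new data; the optional summary would add a table. The downside is that post-baseline values will look slightly lower than under the current rule.
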